4.7. Efficacy Variable

Efficacy will be assessed through the following lipid parameters: calculated LDL-C (using the Friedewald formula), total-C, TG, non-HDL-C (calculated by subtracting HDL-C from Total-C), Apo B, and Lp(a). All lipid parameters will be collected over the course of the study and sent to a central laboratory for evaluation, including scheduled and unscheduled blood draws.

All lipid values obtained during the study (scheduled or unscheduled), regardless of fasting status (fasting or not fasting), can be used to provide a value for the primary and secondary efficacy endpoints, with the following exceptions:

- Only fasting TG measurements will be included in the analysis. TG measurements with missing fasting status will be excluded from the analyses.

All efficacy measurements will be assigned to efficacy analysis windows defined in [Appendix 10.2](#) of this SAP, with the intent to provide an assessment for week 2 to week 16 timepoints for Group A and 2 to week 24 timepoints for Group B. For all time points post-baseline, the value used for the analyses at a given time point (e.g. at week 24) is the value obtained within the corresponding efficacy analysis window. The baseline value is defined as the last available measurement prior to the date of the first double-blind study treatment administration (applicable to measurement derivations during both DBTP and OLTP). For patients randomized and not treated, the baseline value is defined as the last available value prior to the date of randomization.

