8.2.2. Efficacy Procedures

All laboratory samples will be collected before the dose of study drug is administered.

Blood samples for lipid panels should be collected in the morning, in fasting condition (ie, overnight, at least 8 hours fast, only water) for all clinic visits. Alcohol consumption within 48 hours, and smoking or intense physical exercise within 24 hours, preceding blood sampling are discouraged.

Note: If the patient is not in the fasting condition, the blood sample may not be collected and a new appointment can be scheduled the day after (or as close as possible to this date) with a

reminder to be fasted. Patients who are not fasted should 1) be reminded that they should fast, and 2) should be seen by study staff the next day or close as possible in fasted state.

Total-C, HDL-C, TG, ApoB, ApoA-1, Lp(a), and ApoCIII will be directly measured by the central laboratory. LDL-C will be calculated using the Friedewald formula. If TG values exceed 400 mg/dL (4.52 mmol/L), LDL-C will be measured via the beta quantification method (rather than via the Friedewald formula). If the LDL-C value is less than 25 mg/dL (0.65 mmol/L), LDL-C will be measured via the beta quantification method (rather than the Friedewald formula). Non-HDL-C will be calculated by subtracting HDL-C from TC. Ratio ApoB/ApoA-1 will be calculated. All lipid results will be blinded from after randomization until the week 36 visit for the IV cohorts, and until database lock for the SC cohorts. No attempts should be made by the investigator or patient to have the patient's lipid values independently evaluated after randomization and through the EOS visit.

Detailed procedures of sample preparation, storage, and shipment are provided in the laboratory manual.

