4.7.1. Primary Efficacy Variable (s)

The primary efficacy endpoint is the percent change in calculated LDL-C from baseline to week 16 in the intent-to-treat (ITT) population, using the intent-to-treat [ITT] estimand (defined as all LDL-C values regardless of adherence to treatment and subsequent therapies).

The primary endpoint is defined as: $100 \times (\text{calculated LDL-C value at week 16} - \text{calculated LDL-C value at baseline}) / \text{calculated LDL-C value at baseline}$. The baseline calculated LDL-C value will be the last LDL-C level obtained before the first dose of study drug. The calculated LDL-C at week 16 will be the LDL-C level obtained within the week 16 analysis window.

All calculated LDL-C values (scheduled or unscheduled, fasting or not fasting) may be used to provide a value for the primary efficacy endpoint, if appropriate, according to the above definition.

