6.4. Visit Windows

Visit windows will be programmatically imposed on those efficacy and safety measures repeatedly collected over the course of the study. These visit windows are derived from the number of days in study, specifically assigning day ranges to represent the study assessment schedule provided in the protocol. Data analyzed by time point (including efficacy, laboratory safety data, vital signs, and ECG) will be summarized using the analysis windows given in [Appendix 10.2](#) (i.e. efficacy analysis windows for efficacy and global analysis windows for safety). These analysis windows will be applicable for all analyses, and they are defined to provide more homogeneous data for time point-specific analyses. If multiple valid values of a variable exist within an analysis window, the nearest from the targeted study day will be selected for analysis, unless otherwise specified. If the difference is a tie, the value after the targeted study day will be used. If multiple valid values of a variable exist within a same day, then the first value of the day will be selected when time is available, else the scheduled visit will be selected.

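### The SAP's nearest-day rule ignores fasting status, so a non-fasting calculated LDL-C can be analysed in place of a fasting redraw in the same window

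*SAP*

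**What the plan says.** - **Eligible values.** SAP 4.7 sets the general rule: "All lipid values obtained during the study (scheduled or unscheduled), regardless of fasting status (fasting or not fasting), can be used". SAP 4.7.1 repeats it for the primary endpoint: "All calculated LDL-C values (scheduled or unscheduled, fasting or not fasting) may be used to provide a value for the primary efficacy endpoint".
- **Exception for TG.** SAP 4.7 makes one exception: "Only fasting TG measurements will be included in the analysis. TG measurements with missing fasting status will be excluded from the analyses".
- **Choice within a window.** SAP 6.4: "If multiple valid values of a variable exist within an analysis window, the nearest from the targeted study day will be selected for analysis", and "If the difference is a tie, the value after the targeted study day will be used". The rule yields to any other specification, but none elsewhere in the SAP gives fasting samples priority.
- **Windows.** The week 16 efficacy window around day 113 is days 99 to 128 in Group B and days 107 to 126 in Group A (SAP Appendix 10.2).
- **Sampling.** Protocol 8.2.2 asks for a fast of at least 8 hours. For a patient who has eaten, it says the sample may not be taken and a new appointment can be made, and that the patient "should be seen by study staff the next day or close as possible in fasted state".
- **Method.** LDL-C is calculated by Friedewald. Beta quantification replaces it when TG exceeds 400 mg/dL or LDL-C is below 25 mg/dL (Protocol 8.2.2).

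**The concern.** The Friedewald calculation contains TG, so a TG rise after a meal lowers calculated LDL-C with no change in the patient's true level. The plan uses only fasting samples for the TG endpoint but gives the same information no weight when choosing between two LDL-C values in one window. A patient sampled unfasted on day 113 and fasted on day 114 would contribute the day 113 LDL-C and the day 114 TG.

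The rule feeds the primary endpoint and the three week 16 responder endpoints (at least 30% reduction, at least 50% reduction, and LDL-C below 50 mg/dL). The planned sensitivity analyses of the primary endpoint cover stratification errors, on-treatment values, non-GCP sites and missing data (SAP 5.7.1.1). None would show an effect of fasting status.

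**Working it through.** **1. The plan's own figure.** Inputs from SAP 2.2: difference 20, SD 25, two-sided alpha 0.05, power 90%, dropout 5%. A two-sample t-test needs 34 evaluable patients per arm (power 0.9015), and 34 / 0.95 = 35.8, so 36 per arm. The stated 36 is reproduced. The standard error of a difference at 34 per arm is 25 × √(2/34) = 6.1 points.

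**2. When the non-fasting value is selected.** Apply SAP 6.4 (nearest to day 113, ties to the later value) to an unfasted draw on day d and a fasted redraw 1, 2 or 3 days later. The scheduled visit window is ±3 days, so d runs from 110 to 116.

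| Gap to redraw | Fasting redraw selected | Non-fasting value selected |
|---|---|---|
| 1 day | d = 110–112 (3 of 7) | d = 113–116 (4 of 7) |
| 2 days | d = 110–112 (3 of 7) | d = 113–116 (4 of 7) |
| 3 days | d = 110–111 (2 of 7) | d = 112–116 (5 of 7) |

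Over the full week 16 windows with a next-day redraw, the non-fasting value is selected on 15 of 29 possible draw days in Group B and 13 of 19 in Group A. These are counts of days, not probabilities.

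**3. Size in one affected patient.** Assumptions not in the documents: the Friedewald TG term is TG/5 in mg/dL; TG is 30 to 60 mg/dL above fasting; the baseline sample was fasting.

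- LDL-C error: 30/5 = 6 to 60/5 = 12 mg/dL too low.
- Error in percent change = 100 × LDL-C error / baseline. At baseline 100 mg/dL this is 6 to 12 points. At 70 mg/dL it is 6/70 = 8.6 to 12/70 = 17.1 points.
- Responder status: a fasting LDL-C from 50 to just under 56 mg/dL (6 mg/dL error), or just under 62 (12 mg/dL error), would count as below 50. At baseline 100 mg/dL, a true reduction of 24% (or 18%) would count as 30%.

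**4. Size in an arm.** Shift in the arm mean = share affected × error per patient. If 5% of an arm is affected (assumption; 0.05 × 34 = 1.7 patients) at baseline 100 mg/dL, the shift is 0.05 × 6 = 0.3 to 0.05 × 12 = 0.6 points. That is 0.3/6.1 = 5% to 0.6/6.1 = 10% of one standard error of the difference.

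**5. Range for the treatment difference.** The table takes baseline 100 mg/dL, 34 per arm, and the extreme case in which the error occurs only in placebo. The shares and TG rises are assumptions.

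| Share affected | TG rise, mg/dL | Shift in placebo mean | Difference | Power |
|---|---|---|---|---|
| 5% | 20 | 0.05 × 4 = 0.2 | 19.8 | 0.896 |
| 5% | 50 | 0.05 × 10 = 0.5 | 19.5 | 0.887 |
| 10% | 50 | 0.10 × 10 = 1.0 | 19.0 | 0.870 |
| 20% | 100 | 0.20 × 20 = 4.0 | 16.0 | 0.739 |

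If the share affected and the TG rise are equal in both arms, the difference stays at 20 in every row. These are shifts in simple means; the MMRM estimate would differ slightly.

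**The case against.** The strongest reply is that the situation may hardly arise. If the unfasted sample is not taken, which is one course Protocol 8.2.2 describes, only the fasting value exists and nothing competes with it. The wording can be read as permission or prohibition, and no rate is given. This stands, and it makes the point conditional.

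The rule also looks deliberate. SAP 4.7 and 4.7.1 both admit non-fasting LDL-C in plain terms, and Protocol 10.4.3.2 likewise excludes non-fasting measurements for TG only. A reader might infer that the primary endpoint uses a TG input that the SAP itself rejects. The documents do not support that: they exclude non-fasting TG as an analysed variable and nowhere call it unfit for the Friedewald calculation. TG above 400 mg/dL goes to beta quantification, which limits the extreme cases. What remains is an inconsistency between two pre-specified rules, not a breach of either.

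A reader might also infer that the repeat visit is wasted for LDL-C. That is too broad. With a next-day redraw the fasting value already wins for draws on days 110 to 112. Baseline is the last value before first dose, so a pre-dose redraw would be used there.

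Finally, preferring fasting samples without limit has its own cost. It could replace a day 113 value with one 15 days away in Group B or 13 days away in Group A. Group B is also infused at week 16, so a redraw the next day may follow that dose. Both points stand and shape the fix.

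**Conclusion.** The concern holds in conditional form. When an unfasted sample is drawn on or after the target day and a fasted redraw follows within the window, SAP 6.4 selects the non-fasting LDL-C, and no planned analysis would reveal it. (With a three-day gap this also happens for a draw on day 112.)

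The expected effect is small: 0.3 to 0.6 points on an arm mean under the 5% and 30 to 60 mg/dL assumptions, against a standard error of about 6 points. The larger losses in the last table need a 20% share, a 100 mg/dL rise and no error on active treatment, none of which the documents suggest.

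A reader might infer a definite bias against evinacumab. Dilution is plausible, because Protocol 3.2.3 reports TG reductions of up to 80%. But that is a maximum from monotherapy in healthy subjects, and the documents contain no post-meal data on active treatment. Nothing here puts the sample size or the primary conclusion at risk. This is a cheap improvement, not a necessary correction.

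**What to change.** Add one rule to SAP 6.4, for calculated LDL-C only: if the value chosen by the nearest-day rule is non-fasting or of unknown fasting status, and the same window contains a fasting value taken before that visit's dose and within a short stated distance of it (for example 7 days), use the fasting value; otherwise the nearest value stands.

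The distance limit prevents a distant unscheduled sample from replacing one taken on target. The pre-dose condition is met automatically at week 16 in Group A, which has no dose at that visit. In Group B it means that a redraw after the week 16 infusion does not qualify, so the non-fasting value would still be used for that patient.

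The cost is one sentence and one sort key, using the fasting flag that the TG rule already needs. No patient or window is lost. The downside is that the selected value may lie a few days further from the target day. The rule should be fixed before the Group B database lock.

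An acceptable alternative leaves SAP 6.4 unchanged and adds a sensitivity analysis of the primary endpoint restricted to fasting LDL-C, at the price of one more table and some additional missing values.

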4.7.1. Primary Efficacy Variable (s)

The primary efficacy endpoint is the percent change in calculated LDL-C from baseline to week 16 in the intent-to-treat (ITT) population, using the intent-to-treat [ITT] estimand (defined as all LDL-C values regardless of adherence to treatment and subsequent therapies).

The primary endpoint is defined as: $100 \times (\text{calculated LDL-C value at week 16} - \text{calculated LDL-C value at baseline}) / \text{calculated LDL-C value at baseline}$. The baseline calculated LDL-C value will be the last LDL-C level obtained before the first dose of study drug. The calculated LDL-C at week 16 will be the LDL-C level obtained within the week 16 analysis window.

All calculated LDL-C values (scheduled or unscheduled, fasting or not fasting) may be used to provide a value for the primary efficacy endpoint, if appropriate, according to the above definition.

4.7.2. Secondary Efficacy Variable(s)

The secondary efficacy variables include:

- The percent change in Apo B from baseline to week 16 (ITT estimand)
- The percent change in non-HDL-C from baseline to week 16 (ITT estimand)

The percent change in TC from baseline to week 16 (ITT estimand)

- The proportion of patients with $\geq 30\%$ reduction in calculated LDL-C at week 16 (ITT estimand)

The proportion of patients with $\geq 50\%$ reduction in calculated LDL-C at week 16 (ITT estimand)

- Percent change in TGs from baseline to week 16 (ITT estimand)
- Percent change in Lp(a) from baseline to week 16 (ITT estimand)
- Proportion of patients with calculated LDL-C < 50 mg/dL (1.30 mmol/L) at week 16 (ITT estimand)
- Percent change in calculated LDL-C, Apo B, non-HDL-C, TC, TG, and Lp(a) from baseline to week 24 (only applicable to those patients receiving IV route of study treatment administration) (ITT estimand)

4.8. Safety Variables

Patient safety will be assessed through the collection of reported adverse events (AEs), clinical laboratory data, vital signs, and ECG. Unless otherwise noted, the baseline value is defined as the last available value before the first dose of double-blind study treatment.

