10.4.4. Safety Analysis

In general, for the double-blind period, the summary of safety results for patients in the double-blind SAF population will be presented by route of administration (Group A or Group B), pooling the evinacumab dose regimens within each route of administration (Group A or Group B), with the intent to maximize efforts to identify potential safety signals. The treatment group data (individual evinacumab dose regimens and placebo) will also be presented with the intent to support the pooled dose regimens. No formal inferential testing will be performed. Summaries will be descriptive in nature.

For Group B, summaries of safety results for the open-label period will be presented for patients in the open-label SAF, by the total patients administered open-label study treatment (total), as well as by the patient subgroups of study treatment received in the double-blind treatment period (ie, evinacumab dose, placebo).

All safety analyses will use the following common rule:

- The baseline value is defined as the last available value before the first dose of study drug.

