5.7. Analyses of Efficacy Variables

For statistics where international and conventional units do not impact the results (e.g. means and least square (LS) means for percent changes from baseline, statistical testing for both percent and absolute changes from baseline, rates of patients below a threshold), derivations will be calculated and statistical models will be run using conventional units. For other statistics (e.g. descriptive statistics at baseline and over time, absolute changes from baseline), derivations will be presented in both international and conventional units.

Statistical analyses for the primary efficacy endpoints and secondary endpoints will be conducted in the DBTP as described below, and will be completed during the step 1 and 2 efficacy analyses (Section 7). Remaining descriptive efficacy analyses will be completed during step 3. The definition for baseline is applicable to derived variables (e.g., percent change from baseline) in both DBTP and OLTP.

Within each study treatment route of administration (Group A or B), HeFH diagnosis (Yes/No), and high-intensity statin (Yes/No) (high-intensity statin defined as rosuvastatin 20 mg to 40 mg daily, atorvastatin 40 mg to 80 mg daily, or simvastatin 80 mg daily) will be the 2 stratification factors for patient randomization. Stratification factors HeFH diagnosis and high-intensity statin will be accounted for in the statistical modeling for efficacy.

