5.8. Analysis of Safety Data

In general, for the double-blind period, the summary of safety results for patients in the double-blind SAF population will be presented by route of administration (Group A or Group B) and pooling the evinacumab dose regimens within each route of administration (Group A or Group B), with the intent to maximize efforts to identify potential safety signals. The treatment group data (individual evinacumab dose regimens and placebo) will also be presented with the intent to support the pooled dose regimens. No formal inferential testing will be performed. Summaries will be descriptive in nature.

For Group B, summaries of safety results for the open-label period will be presented for patients in the open-label SAF, by the total number of patients administered open-label study treatment (i.e., 15 mg/kg IV), as well as by the patient subgroups of study treatment received in the DBTP (i.e., 5 mg/kg IV, 15 mg/kg IV, or placebo). Summaries will be descriptive in nature.

General common rules

All safety analyses will be performed, unless otherwise specified, using the following common rules:

- For DBTP, safety data in patients who do not belong to the double-blind safety analysis set (i.e., exposed but not randomized) will be listed separately.
- PCSV values are defined as abnormal values considered medically important by the Sponsor according to predefined criteria/thresholds based on literature review and defined by the Sponsor for clinical laboratory tests and vital signs (PCSV version dated January 2009 [[Appendix 10.4](#)]). Considering that the threshold defined in the PCSV list for monocytes and basophils can be below the ULN, the following PCSV criterion will be used for the PCSV analysis of monocytes and basophils:
 - PCSV criterion for monocytes: >0.7 Giga/L or $>ULN$ (if $ULN \geq 0.7$ Giga/L).
 - PCSV criterion for basophils: >0.1 Giga/L or $>ULN$ (if $ULN \geq 0.1$ Giga/L).
- PCSV criteria will determine which patients had at least 1 PCSV during the respective TEAE periods, taking into account all evaluations including unscheduled or repeated evaluations.
- The treatment-emergent PCSV denominator by treatment group for a given parameter will be based on the number of patients assessed for that given parameter at least once during the respective TEAE periods.

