5.8.3. Clinical Laboratory Measurements

The following definitions will be applied to laboratory parameters:

- Double-blind treatment period: The treatment period used for quantitative analysis in the double-blind period is defined as the day after the first study drug administration to the day of the last double-blind study drug injection + 7 days for Group A. For Group B, the treatment period is defined from the day after the first administration of double-blind study treatment to the day of the last administration of double-blind study treatment + 28 days for those patients not proceeding into the open-label treatment period, or up to the day of the first open-label study treatment administration for those patients proceeding into the open-label treatment period.
- Open-label treatment period: The treatment period used for quantitative analysis in the open-label study period is defined from the day after the first dose of open-label study treatment to the day of the last dose of open label study treatment + 28 days.

For respective treatment period (DBTP and OLTP), clinical laboratory parameter actual values (quantitative) and change from baseline values will be descriptively summarized at baseline and each post-baseline visit by at least patient number, mean, median, Q1, Q3, SD, minimum and maximum. Clinical laboratory parameters mean changes from baseline, with the corresponding SE, can be plotted at each visit in the case results warrant further investigation. These parameters will be presented by the biological functions defined in Section 4.8.2. For glucose, only fasting samples will be included in the summaries.

Individual patient laboratory parameter measurements will be additionally evaluated by PCSV criteria (See Appendix 10.4), specifically identifying patients with at least one post-baseline measurement that meets the PCSV criteria within the respective TEAE periods. These laboratory parameters will be presented by the biological functions defined in Section 4.8.2. The incidence of PCSVs at any time during the respective TEAE periods will be summarized regardless of the baseline level, and again according to the following baseline categories:

- Normal (according to PCSV criterion/criteria)/missing
- Abnormal according to PCSV criterion or criteria

Patient listings of laboratory measurements that meet PCSV criteria will be provided for the report appendix. For those laboratory parameters that don't have an associated PCSV criteria,

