6.1. Definition of Baseline for Efficacy/Safety Variables

Unless otherwise specified, the baseline assessment is programmatically as the last available measurement prior to the date of the first double-blind study treatment administration. For patients randomized and not treated, the baseline value is defined as the last available value prior to the date of randomization.

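### For former-placebo patients, open-label safety changes and baseline-dependent PCSVs refer to a value about 24 weeks before their first evinacumab dose, so abnormalities persisting from placebo count as emerging on open-label 15 mg/kg

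*SAP*

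**What the plan says.** **Baseline.** SAP 4.8 defines safety baseline, unless otherwise noted, so that "the baseline value is defined as the last available value before the first dose of double-blind study treatment". SAP 6.1 gives the same anchor for efficacy and safety: "last available measurement prior to the date of the first double-blind study treatment administration". The protocol's common rule for all safety analyses (10.4.4) agrees: "The baseline value is defined as the last available value before the first dose of study drug". The efficacy sections carry this baseline into the open-label period explicitly (SAP 4.7: "applicable to measurement derivations during both DBTP and OLTP"; SAP 5.7: "The definition for baseline is applicable to derived variables"). Those two sentences do not govern safety, but they point the same way.

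**Open-label use.** SAP 5.8.3 states: "For respective treatment period (DBTP and OLTP), clinical laboratory parameter actual values (quantitative) and change from baseline values will be descriptively summarized". SAP 5.8.3 to 5.8.5 define a separate open-label period for laboratory, vital-sign and ECG data but no open-label baseline. SAP 5.9 (HbA1c, hs-CRP, HDL-C) adds none. The exception that SAP 4.8 allows for is therefore never used.

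**PCSVs.** SAP 5.8: "PCSV criteria will determine which patients had at least 1 PCSV during the respective TEAE periods", and the same section calls them treatment-emergent. SAP 5.8.3: "The incidence of PCSVs at any time during the respective TEAE periods will be summarized regardless of the baseline level", and then again by normal/missing or abnormal baseline.

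**Display.** Open-label safety is shown for all patients on 15 mg/kg and by double-blind arm (SAP 5.8).

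**The concern.** For patients already on evinacumab in the double-blind period, the pre-double-blind value is the natural pre-exposure reference. For former-placebo patients it is not. Between that value and their first evinacumab dose lie 24 weeks of placebo, and anything that changed in those weeks and persists is reported under open-label evinacumab.

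The protocol gives the open-label period the job of characterizing long-term safety (3.2.1, 3.2.2). A PCSV table headed treatment-emergent on 15 mg/kg that contains abnormalities predating the drug weakens that purpose, both in the former-placebo column and in the total that pools it.

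**Working it through.** The documents state no figure on this point, so the check traces the rules and then sizes one misplaced case.

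**1. Which outputs depend on baseline.** SAP Appendix 10.4 contains two kinds of criterion:
- Baseline-dependent: ALT, AST, ALP, bilirubin, CPK, percentage rise in creatinine, hemoglobin fall, weight, heart rate, blood pressure, PR, QTc increase.
- Fixed threshold: for example sodium, potassium, HbA1c, albumin, platelets.

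Changes from baseline and the normal/abnormal baseline rows depend on baseline for every parameter.

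**2. What happens on the day of the first open-label dose.**
- SAP 4.8.1: for patients who continue, the double-blind treatment-emergent period ends the day before the first open-label dose. The open-label period starts on the day of that dose.
- SAP 4.8.2: laboratory samples are drawn before dosing.
- Schedule of events, Table 4: the first open-label infusion is at the week 24 visit (Day 169).

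So a former-placebo patient's week 24 pre-dose sample, taken before any evinacumab, falls in the open-label PCSV period and counts as post-baseline. Example: ALT is at or below 3 x ULN before Day 1 and above 3 x ULN in the week 24 pre-dose sample. The criterion is met, the case is entered under open-label 15 mg/kg, and its row is normal/missing at baseline, even if the next sample is normal. If the rise was first seen in that sample, it is not in the placebo double-blind PCSV count at all.

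The quantitative summaries avoid this overlap because their open-label period starts the day after the first open-label dose (SAP 5.8.3).

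**3. Patients concerned.** Protocol 6.1 plans 36 IV placebo and 72 IV evinacumab patients: 36/108 = 33.3%, assuming all enter open label.

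**4. Size per case.** 1/36 = 2.8 points in the former-placebo column; 1/108 = 0.9 points in the total. A mean drift d on placebo appears in full in the former-placebo open-label change and as d x 36/108 = d/3 in the total.

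**5. Illustration by rate.** The documents give no placebo PCSV rate, so the rates are assumed. If all cases arising on placebo persist:

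| Assumed rate on placebo | Cases (36 x rate) | Former-placebo column | Total (cases/108) |
|---|---|---|---|
| 2% | 0.7 | +2 points | +0.7 points |
| 5% | 1.8 | +5 points | +1.7 points |
| 10% | 3.6 | +10 points | +3.3 points |

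With 25% persistence the cases fall to 0.18, 0.45 and 0.9.

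**6. Illustration for weight.** Appendix 10.4 lists a rise of at least 5% and a fall of at least 5% as separate criteria. Assume the 24-week change is normal with mean 0. The share meeting one criterion at week 24 is 1 - Phi(5/SD):
- SD 2%: 1 - Phi(2.50) = 0.6%, or 36 x 0.006 = 0.2 patients
- SD 3%: 1 - Phi(1.67) = 4.8%, or 1.7 patients
- SD 4%: 1 - Phi(1.25) = 10.6%, or 3.8 patients

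These shares describe week 24 before any evinacumab. They are not a net excess, since some of these patients would meet the criterion later in open label under either baseline.

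**The case against.** The rule is pre-specified, consistent between protocol and SAP, and purely descriptive. Former-placebo patients have their own column, listings of values meeting PCSV criteria are required, and actual values are summarized by visit. All of that stands, and it rules out several stronger readings.

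- **A reader might infer that every change arising on placebo is counted as an evinacumab effect.** Only those still present at or after the first open-label dose are. Adverse events are not affected, because they are assigned by onset, worsening or becoming serious within the period (SAP 4.8.1.1).
- **A reader might infer that the former-placebo on-drug change cannot be identified.** For means this goes too far. The week 24 pre-dose value belongs to the double-blind quantitative period, so a later mean minus the week 24 mean approximates it, apart from small differences in who contributes. It is not tabulated, and the subtraction does not work for PCSV incidence or baseline-category tables.
- **A reader might infer that all PCSV counts are inflated.** A fixed-threshold value that persists after week 24 is counted under either baseline, and only its baseline row is wrong.
- **A reader might add the two weight criteria and quote 1.2%, 9.6% or 21%.** They are separate criteria, so the one-sided figures apply.

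Re-baselining also does not supply a control group: background drift during open label would still appear as change on evinacumab.

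What the objection does not answer is the labelling. The separate column isolates these patients without correcting their reference value, the total pools them, and listings leave the sorting to the reader.

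**Conclusion.** The concern holds in limited form. In former-placebo patients, abnormalities that persist from the placebo period, or are present in the week 24 pre-dose sample, are reported as emerging on open-label 15 mg/kg. Their open-label changes and baseline rows use a reference about 24 weeks too early.

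The size is modest: 2.8 points per case in the former-placebo column and 0.9 in the total, for up to 36 of 108 patients. How many cases would occur is unknown, and the rates and SDs used above are assumptions. The primary analysis and the adverse-event tables are untouched. The point is worth correcting because the misattribution follows from the stated rules and the data needed to avoid it are already collected.

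**What to change.** In SAP 4.8 and 5.8, for patients randomized to IV placebo:
1. Define an open-label baseline as the last value before the first open-label infusion. Word it to include the pre-dose sample of that day, as Appendix 10.2 already does for Day 1.
2. Use it for open-label change from baseline, for the baseline conditions in PCSV criteria, and for the normal/abnormal baseline categories.
3. Count only values taken after that infusion as open-label PCSVs.

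Keep the double-blind baseline for patients already on evinacumab, and label the baseline used in each open-label column, including the total. SAP 1 has the final plan issued before the first-step database lock, so the change belongs before that lock.

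**Cost.** One derived baseline from data already collected, some extra or relabelled open-label tables, and two baseline definitions to explain. Columns using different baselines need care when compared, and drift within the uncontrolled open-label period remains.
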